4.6.3 Clinical Laboratory, Blood Sample

4.6.3.1 Definitions and Derivations

Blood samples for determination of clinical chemistry and haematology will be collected according to the schedule of activities in Section 1.3 of the CSP. Clinical Safety Laboratory Assessments are listed in Section 8.2.4 of the CSP.

Treatment emergent abnormalities

Treatment emergent abnormalities in selected parameters for haematology and chemistry laboratory measurements are defined as post-baseline measurements meeting the pre-defined criteria for abnormality below and is more extreme than the non-missing baseline value for a subject. Thus, if the baseline value met the criteria for marked abnormality and the post-baseline value is equal to or less extreme than the baseline value, this is not considered a treatment emergent abnormality. Low and high ranges are derived based on reference ranges provided by the central laboratory, if available.

- Haematology:

- Eosinophils $\geq 0.7 \times 10^9/L$; $\geq 1.5 \times 10^9/L$
- Haemoglobin $< 100 \text{ g/L}$; $< 80 \text{ g/L}$
- Neutrophils $< 1.5 \times 10^9/L$; $< 1.0 \times 10^9/L$
- White blood cell count $< 3.0 \times 10^9/L$; $< 2.0 \times 10^9/L$
- Chemistry:
 - Creatinine: $\geq 1.5 \times \text{baseline creatinine}$ and $\geq 2 \times \text{baseline creatine}$
 - ALP $> 1.5 \times \text{ULN}$; $> 3 \times \text{Upper limit normal (ULN)}$
 - ALT $> 3 \times \text{ULN}$; $> 5 \times \text{ULN}$; $> 10 \times \text{ULN}$
 - AST $> 3 \times \text{ULN}$; $> 5 \times \text{ULN}$; $> 10 \times \text{ULN}$
 - TB $> 1.5 \times \text{ULN}$; $> 2 \times \text{ULN}$
 - AST or ALT $> 3 \times \text{ULN}$
 - AST or ALT $> 3 \times \text{ULN}$ and TB $> 2 \times \text{ULN}$
 - TSH $> 6 \text{ mIU/L}$; $\geq 10 \text{ mIU/L}$
 - TSH $> 6 \text{ mIU/L}$ and free T4 $< \text{Lower limit normal (LLN)}$; $\geq 10 \text{ mIU/L}$ and free T4 $< \text{LLN}$

For criteria comprising combinations of parameters, the treatment emergent abnormality is flagged when both parameters meet their individual criteria on same visit.

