Appendix E Actions Required in Cases of Increases in Liver Biochemistry and Evaluation of Hy's Law

E 1 Introduction

This Appendix describes the process to be followed in order to identify and appropriately report PHL and HL cases. It is not intended to be a comprehensive guide to the management of elevated liver biochemistries.

During the course of the study the investigator will remain vigilant for increases in liver biochemistry. The investigator is responsible for determining whether a participant meets potential PHL criteria at any point during the study.

All sources of laboratory data are appropriate for the determination of PHL and HL events; this includes samples taken at scheduled study visits and other visits including central and all local laboratory evaluations even if collected outside of the study visits; for example, PHL criteria could be met by an elevated ALT from a central laboratory **and/or** elevated TBL from a local laboratory.

The investigator will also review Adverse Event data (for example, for AEs that may indicate elevations in liver biochemistry) for possible PHL events.

The investigator participates, together with AZ clinical project representatives, in review and assessment of cases meeting PHL criteria to agree whether Hy's Law (HL) criteria are met. HL criteria are met if there is no alternative explanation for the elevations in liver biochemistry other than Drug Induced Liver Injury (DILI) caused by the IP.

The investigator is responsible for recording data pertaining to PHL/HL cases and for reporting SAEs and AEs according to the outcome of the review and assessment in line with standard safety reporting processes.

E 2 Definitions

Potential Hy's Law

Aspartate Aminotransferase or ALT $\geq 3 \times$ ULN **together with** TBL $\geq 2 \times$ ULN at any point during the study following the start of study medication irrespective of an increase in ALP.

Hy's Law

AST or ALT $\geq 3 \times$ ULN **together with** TBL $\geq 2 \times$ ULN, where no other reason, other than the IMP, can be found to explain the combination of increases, eg, elevated ALP indicating cholestasis, viral hepatitis, another drug.

For PHL and HL the elevation in transaminases must precede or be coincident with (ie, on the same day) the elevation in TBL, but there is no specified timeframe within which the elevations in transaminases and TBL must occur.

E 3 Identification of Potential Hy's Law Cases

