In order to identify cases of PHL it is important to perform a comprehensive review of laboratory data for any participant who meets any of the following identification criteria in isolation or in combination:

- ALT $\geq 3 \times$ ULN
- AST $\geq 3 \times$ ULN
- TBL $\geq 2 \times$ ULN

Central Laboratories Being Used:

When a participant meets any of the PHL identification criteria, in isolation or in combination, the central laboratory will immediately send an alert to the investigator (also sent to AZ representative).

The investigator will also remain vigilant for any local laboratory reports where the PHL identification criteria are met, where this is the case the investigator will:

- Notify the AZ representative
- Request a repeat of the test (new blood draw) by the central laboratory without delay
- Complete the appropriate unscheduled laboratory eCRF module(s) with the original local laboratory test result

When the identification criteria are met from central or local laboratory results the investigator will without delay:

- Determine whether the participant meets PHL criteria (see Section E 2 for definition) by reviewing laboratory reports from all previous visits (including both central and local laboratory results)

E 4 Follow-up

E 4.1 Potential Hy's Law Criteria not met

If the participant does not meet PHL criteria the investigator will:

- Inform the AZ representative that the participant has not met PHL criteria.
- Perform follow-up on subsequent laboratory results according to the guidance provided in the Clinical Study Protocol.

E 4.2 Potential Hy's Law Criteria met

If the participant does meet PHL criteria the investigator will:

- Notify the AZ representative who will then inform the central Study Team.
- Within 1 day of PHL criteria being met, the investigator will report the case as an SAE of Potential Hy's Law; serious criteria 'Important medical event' and causality assessment 'yes/related' according to CSP process for SAE reporting.
- For participants that met PHL criteria prior to starting IMP, the investigator is not required to submit a PHL SAE unless there is a significant change[#] in the participant's condition.
- The Study Physician contacts the investigator, to provide guidance, discuss and agree an approach for the study participants' follow-up (including any further laboratory testing) and the continuous review of data.
- Subsequent to this contact the investigator will:

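### Does the SAP's same-visit liver row understate potential Hy's Law cases?

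*SAP*

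**What the plan says.** SAP 4.6.3.1 lists its treatment-emergent laboratory abnormalities under one heading. There are single-parameter rows for ALT, AST and total bilirubin, a row for either transaminase above 3×ULN, and a combined row for AST or ALT above 3×ULN with bilirubin above 2×ULN. Post-baseline values count when "meeting the pre-defined criteria for abnormality below and is more extreme than the non-missing baseline value for a subject". For every combined criterion, including TSH with free T4, "the treatment emergent abnormality is flagged when both parameters meet their individual criteria on same visit". On reference limits: "Low and high ranges are derived based on reference ranges provided by the central laboratory, if available".

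SAP 4.6.3.2 then plans counts of subjects for each criterion, a display of maximum ALT and AST against maximum bilirubin by arm, and key subject information for the 4.6.3.1 abnormalities. A separate paragraph adds key subject information, paged by treatment group, for subjects meeting PHL criteria. It neither restates those criteria nor says where they are defined.

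Protocol Appendix E 2 defines PHL as AST or ALT at or above 3×ULN together with bilirubin at or above 2×ULN, at any time after study medication starts. On order, "the elevation in transaminases must precede or be coincident with (ie, on the same day) the elevation in TBL"; on timing, "there is no specified timeframe within which the elevations in transaminases and TBL must occur". There is no baseline condition. Appendix E 1 admits "central and all local laboratory evaluations even if collected outside of the study visits".

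**The concern.** The combined row uses the same 3× and 2× multiples as PHL, and it is the only combined transaminase and bilirubin rule written out in the SAP. It is also the only planned laboratory table line that gives a per-arm number for the pair. A reader could take that number for the PHL count, and a programmer could reuse the rule for the PHL subject information.

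In Part A the safety laboratory visits after Week 24 are at Weeks 36, 48 and 52, so a transaminase rise followed by a bilirubin rise can easily fall at two visits. If the row were the trial's measure of PHL, serious liver signals could be missing from one arm's count.

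**Working it through.** No figure in the plan is at issue, so the check compares the two rules and then follows a test case through the planned outputs.

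**The rules side by side**

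| Feature | SAP 4.6.3.1 row | Protocol PHL | Effect |
|---|---|---|---|
| Thresholds | >3× and >2×ULN | ≥3× and ≥2×ULN | Only for values exactly at a limit |
| Timing | Same visit | Transaminase first or same day, any gap | Sequential rises are PHL only |
| Baseline | More extreme than baseline | No condition | Can bind for bilirubin; seldom for transaminases, since Part A exclusion 18 removes ALT or AST ≥2×ULN at Screening |
| Laboratory source | Reference ranges from the central laboratory, if available | Central and local results | No difference shown |

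The last line is not a real difference. The SAP sentence fixes the source of the ranges and does not exclude local results. Protocol 8.2.4 has clinical chemistry run centrally. For a qualifying local result, Appendix E 3 tells the investigator to "Request a repeat of the test (new blood draw) by the central laboratory without delay" and to "Complete the appropriate unscheduled laboratory eCRF module(s) with the original local laboratory test result".

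**Direction of the difference**

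Take two post-baseline visits, ALT in {1, 3, 3.5}×ULN, bilirubin in {1, 2, 2.5}×ULN, baseline ALT 1×ULN and baseline bilirubin 1 or 2.5×ULN. These values are assumptions chosen to exercise each rule; the counts are not event rates.

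- Profiles: 9 × 9 × 2 = 162.
- PHL: ALT raised at the first visit and bilirubin raised at either visit, 6 × 8 = 48; ALT raised only at the second visit with bilirubin raised there, 2 × 6 = 12. So (48 + 12) × 2 = 120.
- SAP row with baseline bilirubin 1×ULN: 81 − 8 × 8 = 17. With baseline 2.5×ULN: 0, because no value exceeds baseline. Total 17.
- All 17 are also PHL.

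The row is therefore a subset of PHL when ALT and bilirubin are drawn on the same day within a visit. If values from different days fall in one analysis visit with bilirubin first, the row could flag a subject whom the order rule excludes.

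**A test case**

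ALT is 4×ULN on Day 169 (Week 24) and below 3×ULN on Day 253 (Week 36), when bilirubin is first 2.5×ULN. Baseline values are assumed normal.

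- Combined row: 0, because the two criteria are not met at one visit.
- PHL under Appendix E 2: met.
- Single-parameter rows: counted under ALT >3×ULN, AST or ALT >3×ULN, TB >1.5×ULN and TB >2×ULN, each with key subject information.
- Maximum-versus-maximum display: plotted at 4 and 2.5×ULN in the On-study version.
- PHL key subject information: included.
- Adverse events: Appendix E 4.2 requires an SAE report within 1 day, so the subject enters the by-arm SAE tables and receives a narrative (SAP 4.6.2.2).

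The On-treatment outputs depend on the last dose, because that period ends 14 days after it (SAP 3.3.1.5). If study drug stopped on Day 169, the period ends on Day 169 + 14 = 183, before Day 253, and the bilirubin value is On-study only. It is On-treatment if the last dose is on or after Day 253 − 14 = 239. This follows from the period definitions and applies to any late laboratory value.

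**The case for a change.** The strongest case for a change is that none of the other outputs is a clean PHL count. The maximum-versus-maximum display ignores order: bilirubin raised first and ALT later plots in the same region without meeting Appendix E 2. SAE terms can be revised under Appendix E 5 once an alternative explanation is agreed. Key subject information has to be counted by hand, and its criteria are the ones the SAP leaves unstated. The SAP also does not say whether one or both members of a pair must exceed baseline.

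These observations are correct, but they do not show that the plan would mislead. SAP 4.6.3.2 gives key subject information for the 4.6.3.1 abnormalities and then, separately, for PHL. If PHL meant the combined row, the second paragraph would be redundant. Among the plan documents only Appendix E 2 defines the term, and the SAP Introduction sends the reader to the protocol. An analyst would therefore use Appendix E 2.

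A new PHL row would bring its own problems. It would need a rule for dating a two-visit case to an analysis period, which neither document contains, and a local ULN that the documents do not say is recorded. It would also be a further number that need not match the PHL subject information or the reported SAEs.

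**Conclusion.** No change to the plan is needed. The row is narrower than PHL on thresholds, timing and baseline, but it sits under its own heading with its rules stated, and PHL is handled separately. Followed as written, the plan loses no PHL case. Safety analyses are descriptive (Protocol 9.4.3), and no decision rule in the documents rests on the row.

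The gap between the row and the number of PHL subjects cannot be sized from the documents and may be zero. The conclusion assumes that PHL in SAP 4.6.3.2 is read as Appendix E 2, and that investigators report PHL cases as Appendix E 4.2 requires. Citing Appendix E 2 there, or footnoting the row as same-visit only, would be harmless editing; no result depends on it.

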4.6.3.2 Presentations

Clinical laboratory parameters will be presented for SAS by treatment group, and scheduled visit, separately for haematology and chemistry parameters, and the parameters will be presented in alphabetical order.

Values and absolute change from baseline will be presented for continuous variables using descriptive statistics for all scheduled assessments after baseline.

Maximum on-treatment/on-study ALT and AST versus maximum on-treatment/on-study total bilirubin will be presented, by treatment group

Treatment emergent abnormalities

The number of subjects with observations meeting the pre-specified abnormality laboratory criteria in Section 4.6.3.1 for each parameter will be presented, for SAS.

Key subject information

Key subject information will be presented for subjects with treatment emergent abnormalities as defined and listed in Section 4.6.3.1.

Subjects meeting potential Hy's laws criteria will be presented as key subject information, with treatment group presented by page.

Listings

A listing of individual laboratory measurements, including reference range indicator will be presented.

4.6.4 Clinical Laboratory, Urinalysis

4.6.4.1 Definitions and Derivations

Clinical laboratory parameters for urinalysis collected according to the schedule of activities according to Section 1.3 of the CSP. Clinical Safety Laboratory Assessments are listed in Section 8.2.4 of the CSP.

Treatment emergent abnormalities

Subjects with treatment emergent urinalysis parameter abnormalities in quantitative parameters will be defined according to the non-mutually exclusive thresholds based on central laboratory ranges (when applicable): <LLN, >ULN.

4.6.4.2 Presentations

Clinical laboratory parameters for urinalysis will be presented for SAS by treatment group, and the parameters will be presented in alphabetical order.

Change from baseline to maximum and minimum assessment on-treatment and on-study respectively will be presented in shift tables.

Treatment emergent abnormalities

The number of subjects with observations meeting the pre-specified abnormality laboratory criteria in Section 4.6.4.1, for each parameter will be presented, for SAS.

4.6.5 Other Laboratory Evaluations

4.6.5.1 Definitions and Derivations

Treatment emergent abnormalities

Treatment emergent ANCA positivity is defined as shifts from negative at baseline to positive post-treatment.

‘Negative’ results will be mapped to negative category. Results not reported as ‘Negative’ will be mapped to positive category.

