8.2.4 Clinical Safety Laboratory Assessments

Blood and urine samples for determination of clinical chemistry, haematology, and urinalysis will be taken at the visits indicated in the SoA (See Section 1.3).

Additional safety samples, including ANCA samples, may be collected if clinically indicated at the discretion of the investigator. The date, time of collection, and type of sample will be recorded on the appropriate eCRF.

The clinical chemistry and, haematology, will be performed at a central laboratory. Dipstick urinalysis will be performed locally.

The following laboratory variables will be measured:

Table 8 Laboratory Safety Variables

Haematology/Haemostasis (whole blood)	
B-Hb	B-Leukocyte differential count (absolute count and percent differential)
B-Leukocyte count	B-Platelet count
haematocrit	MCV
MCHC	MCH
RDW	reticulocyte
Clinical Chemistry (serum or plasma)	
S-Creatinine	S-Albumin
S-Bilirubin, total	S-Potassium
S-Bilirubin, direct	
S-Bilirubin, unconjugated, ie, indirect (total – direct)	S-Calcium, total
S-ALP	S-Sodium
S-AST	S-Creatine kinase
S-ALT	Glucose
Free T4 and total T4	Chloride
T3	Bicarbonate

Table 8 Laboratory Safety Variables

TSH	Phosphorus
Magnesium	S-Uric Acid ^a
Urinalysis (dipstick)	
U-Hb/Erythrocytes/Blood	U-Glucose
U-Protein/Albumin	
Immunology	
c-ANCA ^b	p-ANCA
Other assessments	
FSH (females only, at screening)	

^a Serum samples sent to the central laboratory for serum uric acid safety assessment will also be used as part of the exploratory biomarker assessment at Visit 3, Visit 8, and Visit 11/EDV (Part A).

^b The ANCA sample collected at baseline is only to be tested upon requirement ie, appearance of maculopapular rash, based on investigator discretion. An additional sample should be collected if clinically indicated.

ALP, alkaline phosphatase; ALT, alanine aminotransferase; AST, aspartate aminotransferase; B, whole blood; c-ANCA, cytoplasmic staining anti-neutrophil cytoplasmic antibodies; FSH, follicle-stimulating hormone; Hb, haemoglobin; MCH, mean corpuscular haemoglobin; MCHC, mean corpuscular haemoglobin concentration; MCV, mean corpuscular volume; p-ANCA, perinuclear-anti-neutrophil cytoplasmic antibodies; RDW, red cell distribution width; S, serum; T3, triiodothyronine; T4, thyroxine; TSH, thyroid stimulating hormone; U, urine.

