- Death: With the exception of assessment of mortality, will be handled hypothetically as it cannot occur, implemented by censoring time to event data at death and not imputing any data after death.

Population level summaries: Distribution of endpoints by treatment group, Kaplan-Meier estimate for endpoints by treatment group, difference in Kaplan-Meier estimates between treatment groups and treatment hazard ratios.

This estimand requires that to the extent possible, randomised subjects are followed up regardless of study intervention compliance and adherence to the study protocol.

Adverse Events

All AEs will be classified by system organ class, high level group term, high level term, and preferred term according to MedDRA.

AEs will be presented for each treatment group by SOC and/or PT, covering number and percentage of subjects reporting at least one event. An overview of AEs will present for each treatment group the number and percentage of subjects with any AE, AEs with outcome of death, serious AEs, and AEs leading to discontinuation of IP. Separate AE tables will be provided taking into consideration seriousness, death, and events leading to discontinuation of IP. An additional table will present number and percentage of subjects with most common AEs. Most common (eg, frequency of $>x\%$, $\geq x\%$) will be defined in the SAP. In accordance with the requirements of the FDA, a separate table will present non-serious AEs occurring in more than 5% of subjects in any treatment group. Key subject information will be presented for subjects with AEs with outcome of death, serious AEs, and AEs leading to discontinuation of IP. An AE listing for the safety analysis set will cover details for each individual AE. AEoSIs related to skin reactions, including maculopapular rash, and infection will be presented. Full details of AE analyses will be provided in the SAP.

All safety analyses are descriptive; hence no p-values will be presented for any safety analyses, and confidence intervals are provided as an illustration of precision of the estimate. Hazard ratio between treatment groups will be based on a Cox proportional hazards regression model with a factor for treatment group.

Treatment emergent

For Part A, the definition for treatment emergent events will be provided in the SAP.

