4.6.5.2 Presentations

Treatment emergent abnormalities

The number of subjects with treatment emergent ANCA positivity will be presented in a shift table with the categories positive and negative, by treatment group.

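### If Table 8 footnote b applies to Part A, the ANCA shift table can classify only participants whose baseline sample was tested on requirement, such as after a rash, so its by-arm counts are incomplete and not comparable

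*SAP*

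**What the plan says.** The SAP, which covers Part A only, defines the safety variable in 4.6.5.1: "Treatment emergent ANCA positivity is defined as shifts from negative at baseline to positive post-treatment". Results reported as Negative go to the negative category, and every other result "will be mapped to positive category". Section 4.6.5.2 adds that the number of subjects with treatment-emergent positivity "will be presented in a shift table with the categories positive and negative, by treatment group". Neither section says what happens when the baseline was not tested, and neither names a denominator.

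The protocol controls when the baseline sample is assayed. Footnote b to Table 8 (section 8.2.4) reads: "The ANCA sample collected at baseline is only to be tested upon requirement ie, appearance of maculopapular rash, based on investigator discretion". Footnote a, next to it, is marked as applying to Part A; footnote b names no part.

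The Part A schedule of activities (protocol Table 1) has an ANCA sample at Visit 3 (baseline) and one at a late visit, for all participants. The text read from the PDF does not settle whether the late column is Visit 11/EDV or Visit 12. The Part B schedule (Table 2) has ANCA at randomisation only. Beyond the schedule, section 8.2.4 allows: "Additional safety samples, including ANCA samples, may be collected if clinically indicated at the discretion of the investigator".

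**The concern.** A shift from baseline can be counted only where both ends were measured. In Part A the late end is scheduled for everyone. If footnote b applies, the baseline end is assayed only after a trigger. Protocol Table 3 lists that trigger, maculopapular rash, as an identified risk of AZD4831. Entry to the table would then depend on an event that occurs after randomisation and is expected more often on active drug, and also on the investigator's choice.

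Two things follow. First, conversions in participants without rash would mostly be missing from the count in every arm. Second, the number of classifiable pairs would differ between arms because of treatment, so a difference in counts could appear or disappear for reasons unrelated to ANCA. A reader of the study report would see a by-arm table of treatment-emergent positivity with nothing to show that most participants could not have contributed to it.

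**Working it through.** The documents give no ANCA figure, so there is nothing to reproduce. The check sets the texts side by side and then adds an illustration on stated assumptions.

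**Who can be classified if footnote b applies to Part A**

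| Participant | Baseline result | Late result | Classifiable under SAP 4.6.5.1 |
|---|---|---|---|
| No rash or other requirement | Generally none | Scheduled | No |
| Rash, investigator requests the assay | Yes | Scheduled or extra sample | Yes |
| Rash, investigator does not request it | None | Scheduled or extra sample | No |

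The general SAP rules do not change this. Section 3.3.1.3 says missing safety laboratory data are not imputed. Section 3.3.1.7 says missing observations are counted when appropriate and left out of percentage denominators. An untested baseline is therefore missing, not misclassified, but the remaining pairs are still a selected set.

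**Illustration (not an estimate of the size)**

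Inputs from the documents:
- 660 randomised 1:1:1, so 660 / 3 = 220 per arm.
- Rash at 5 mg: 1/27 = 3.7% (Phase 2a, protocol Table 3) and 2/12 = 16.7% (Japanese and Chinese healthy volunteers, protocol 4.3).

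Assumptions not in the documents:
- Rash on placebo of 0.5% to 2%.
- True ANCA conversion s = 5% (range 2% to 10%), equal in all arms and independent of rash.
- A baseline assay for every rash case and for nobody else.

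Formulas: baselines tested = 220 × rash rate; countable cases = 220 × rash rate × s; true cases = 220 × s.

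| Arm and rash rate | Baselines tested | Without a baseline result | Countable cases, s = 5% | Chance of none countable |
|---|---|---|---|---|
| 5 mg, 1/27 | 8.1 | 96.3% | 0.41 | 0.67 |
| 5 mg, 2/12 | 36.7 | 83.3% | 1.83 | 0.16 |
| Placebo, 0.5% | 1.1 | 99.5% | 0.06 | 0.95 |
| Placebo, 2% | 4.4 | 98.0% | 0.22 | 0.80 |

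True cases are 220 × 0.05 = 11 in each arm (4.4 at s = 2%, 22 at s = 10%). The ratio of expected counts equals the ratio of rash rates, because s cancels: from (1/27) / 0.02 = 1.85 up to (2/12) / 0.005 = 33.3, although the true ratio is 1. The expected counts are so small that the more likely practical result is a nearly empty table that looks reassuring.

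If conversion really were independent of rash, the proportion among tested pairs would still be s in each arm. The distortion would then be in the counts, and in any percentage taken over the whole arm. If conversion and rash are related, the pairs do not represent the arm either. In neither case do the pairs form a randomised comparison.

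**The case against.** **Footnote b may have been meant for Part B.** It describes one baseline sample held until needed, plus an extra sample if indicated, and that matches the Part B schedule. It came in with the current amendment, which is largely the Part B redesign and lists it as a clarification. This reading is plausible, but nothing in the text limits the footnote to Part B. In the extracted table its mark sits on c-ANCA only, although its wording covers the ANCA sample as a whole.

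**Part A baselines may already have been tested.** The history entry for Amendment 1 lists the ANCA samples to be measured only if useful, and baseline is not among them. Part A was randomising before the change. Section 8.2.4 also describes the assay without restricting it to rash. This stands as a possibility; the documents do not say what was done. A reader might infer that the table can hold rash cases only. That goes further than the documents allow.

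**The output is minor.** Protocol 9.4.3 says: "All safety analyses are descriptive; hence no p-values will be presented for any safety analyses". ANCA is not an adverse event of special interest, and the legible parts of the risk table do not list it. A reader might take the follow-on MPO and proteinase 3 assays as showing an established safety signal, but the documents describe them only as laboratory workflow. No formal test is biased.

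**The mapping rule may be harmless.** Positive samples receive titres, so sending every result other than Negative to positive may simply be a way to capture titres. No section mentions an indeterminate ANCA result. A reader might infer that the rule creates false positives, but that is hypothetical.

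**A single rash rate gives a false size.** Assuming 5%, for example, would suggest that 95% have no baseline result. The documents give 3.7% and 16.7% at 5 mg in two different populations, and footnote b leaves testing to the investigator.

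**Conclusion.** The conflict between the two documents is real but conditional. As the texts stand, SAP 4.6.5.1 needs a baseline ANCA result that footnote b withholds from most participants, and no wording exempts Part A. If footnote b does apply to Part A, a late positive without rash generally cannot be classified, and the by-arm counts are incomplete and not comparable because a treatment-related event selects the pairs. If it does not apply, or if Part A baselines were in fact assayed routinely, the problem shrinks to unclear wording.

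The size cannot be derived. It depends on the scope of footnote b, the number of Part A baselines tested, rash on placebo, and the rate of ANCA conversion, and the documents supply none of these. The illustration shows the direction only. The consequence is confined to one descriptive shift table, and the efficacy analyses are untouched. It is still worth correcting, because the table would otherwise be read as covering the whole arm.

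**What to change.** 1. Reconcile Table 8 footnote b with SAP 4.6.5 by stating which study part the footnote covers.
2. For Part A, assay the stored baseline sample, blind to arm, for every participant with a non-negative post-baseline ANCA result. Cases can then be identified the same way in all arms. Under the assumptions above, and with a late result for everyone, all 220 × s true cases per arm become classifiable, with an expected ratio of 1.0 when there is no effect.
3. In SAP 4.6.5.2, report by arm the post-baseline positives with the number tested, the number with a tested baseline and post-baseline pair as the shift-table denominator, and a row for baseline not tested. Because the extra baselines are chosen by a later non-negative result, read the treatment-emergent count against the number with a post-baseline test, not as a percentage of pairs.
4. As a minor safeguard in SAP 4.6.5.1, state that not-done or unusable ANCA records are missing and are not mapped to positive.

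The cost is a few extra assays on samples already collected, plus wording. Testing every Part A baseline would complete all cells of the shift table, at up to about 660 assays; that is not needed to identify the cases.
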